## 27 August 2020

# 8. STUDY PROCEDURES/EVALUATIONS

## 8.1. Clinical Evaluations

Medical history: history or presence of prior and current medical conditions or significant surgical procedures

Physical exam: overall physical assessment (to include vital signs [temperature, blood pressure, respiratory rate, heart rate, peripheral oxygen saturation], skin, head and neck, lungs, heart, liver, spleen, extremities, lymph nodes, and nervous system) and weight will be collected at Screening, Baseline (Day - 1 to Day 1) and Day 2 (day of discharge). Height will be measured and BMI calculated at screening only.

ECG: performed in the supine or semi-recumbent position after resting for at least 10 minutes at 3 timepoints: Screening, Baseline (Day -1 to Day 1), and Day 2 within 2 hours of the third (last) dose of study drug. Each ECG will be interpreted and abnormal results acted upon by the investigator as outlined for each timepoint (Screening and Baseline ECG abnormalities per Exclusion Criteria, Day 2 ECG abnormalities per Appendix B). In case of premature discontinuation, ECG will be performed before discharge.

Vital signs: heart rate, blood pressure, temperature, respiratory rate, and peripheral oxygen saturation will be measured with the subject in the supine or semi-recumbent position, will be obtained at the following timepoints: Screening, Baseline (Day -1 to Day 1), before each of 3 doses of study medication, approximately at 0.5, 1, 2, and 5 hours after the start of each infusion of study drug, and before discharge from DEPRU on Day 2. Since changes in vital signs are expected during bronchoscopy, when a vital sign timepoint is scheduled during a subject's bronchoscopy, that timepoint will be measured immediately before the start of bronchoscopy. If vital signs are abnormal, repeat readings will be obtained up to twice more (total of 3 measurements including the first one), 5-10 minutes apart. If they remain abnormal, unscheduled vital signs will be repeatedly obtained until they normalize (at investigator's discretion).

Prior/Concomitant Medications/Treatments: information regarding allergies and use of prescription medications, non-prescription medications, herbal supplements, nicotine, caffeine, alcohol, and illicit drugs will be obtained at Screening, Baseline (Day -1 to Day 1), Treatment (Days 1-2), Day 2 before discharge, and throughout each subject's enrollment as required.

# 8.2. Laboratory Evaluations

#### 8.2.1. Clinical Laboratory Evaluations

Serum chemistry: albumin, glucose, blood urea nitrogen (BUN), potassium, magnesium, calcium, sodium, total protein, creatinine, triglycerides, total cholesterol, creatine phosphokinase (CPK), phosphorus, alkaline phosphatase (ALP), AST, ALT, total bilirubin, direct bilirubin, and lactate dehydrogenase (LDH) will be collected at Screening and Day 2 before discharge. Albumin, glucose,

DMID/NIAID/NIH

DMID Protocol 16-0058	Version 9.0
IV Fosfomycin PK Study	27 August 2020

BUN, potassium, magnesium, calcium, sodium, phosphorus, total protein, creatinine, CPK, ALP, AST, ALT, and total bilirubin will be collected at Baseline (Day -1 to Day 1). Sodium, potassium, magnesium, calcium, and phosphorus will be collected approximately 2 hours prior to the assigned bronchoscopy timepoint.

Hematology: CBC with differential (hemoglobin, hematocrit, platelet count, white blood cell (WBC) count, neutrophils, lymphocytes, monocytes, eosinophils, basophils) will be collected at Screening and Day 2 before of discharge.

Coagulation: PT and aPTT will be collected at Screening and Day 2 before discharge.

Urinalysis: leukocyte esterase, blood, pH, specific gravity, glucose, protein. A microscopic test will be performed if urinalysis is abnormal. The microscopic urinalysis result for the presence of blood will supersede the dipstick urinalysis result. Urinalyses will be performed at Screening and Day 2 before discharge.

Serum and urine pregnancy test: a serum pregnancy test will be performed on all females of childbearing potential at Screening, a urine pregnancy test will be performed on all females of childbearing potential at Baseline (Day -1 to Day 1).

Test for SARS-CoV-2 (COVID-19) at Screening or Baseline (Day -1 to Day 1) within 72 hours of admission

Screening for Chronic Infections: HIV antibody, HBsAg, and HCV antibody will be measured at screening

Alcohol (breathalyzer) test, urine cotinine, and urine drug testing: performed at Screening and Baseline (Day -1 to Day 1). Urine will be collected and tested separately for cotinine and illicit drugs: barbiturates, benzodiazepines, THC, cocaine, opiates, and amphetamine/methamphetamine.

Urea: a blood sample for plasma urea concentration will be obtained just before or during each subject's scheduled bronchoscopy.

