#### DMID/NIAID/NIH

#### CONFIDENTIAL

sampling time. Ten additional enrolled subjects will act as alternates to obtain 30 evaluable subjects.

Each subject will complete Screening, Baseline, Treatment and Follow-up Phases. The Screening Phase will be conducted on an outpatient basis within 30 days of the Baseline Phase, which will consist of admission to DEPRU on the day before the first dose (Day -1) for pre-dosing assessments. The Treatment Phase will start on the day of first dose (Day 1) and end at the time of discharge from DEPRU. Three IV doses of ZTI-01 will be administered every 8 hours (hours 0, 8, and 16 during the Treatment Phase). Blood samples for PK measurements will be collected before each dose, up to 8 hours after the start of the first IV infusion of ZTI-01, and up to 12 hours after the start of the third IV infusion (Tables 2 and 3). One bronchoscopy with BAL will be completed on each subject at the timepoint to which that subject was randomized. Key electrolytes will be remeasured prior to each subject's bronchoscopy in order to minimize risk of arrhythmia. Subjects will be discharged following the final 12-hour blood sampling time point (if safety parameters are acceptable to the Investigator). Safety assessments will be conducted during the entire 24-hour Treatment Phase. The Follow-Up Phase consists of a telephone interview on Day 3 for symptom-driven safety assessments.

Estimated Time to Complete	
Enrollment:	

Approximately 12 weeks

DMID/NIAID/NIH

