#### 8.2.2. Bronchoscopy and Bronchoalveolar Lavage (BAL)

Each subject will be assigned to one bronchoscopy sampling timepoint. The bronchoscopy sampling times will be at 30 minutes, 1 hour 15 minutes, 2, 5, and 8 hours from the start time of the third (last) infusion of ZTI-01. A total of 6 subjects will be assigned to each of the five BAL sampling times.

Sodium, potassium, magnesium, calcium, and phosphorus will be measured approximately 2 hours prior to each subject's bronchoscopy timepoint. Subjects with grade 2 or higher abnormalities (Appendix B) in these electrolytes will not receive any further study product and will not undergo bronchoscopy.

Bronchoscopy will be performed in a standardized fashion according to the MOP. Topical lidocaine will be applied to the upper airways to prepare subjects for bronchoscopy. If needed, 1.0% percent lidocaine

CONFIDENTIAL

DMID Protocol 16-0058	Version 9.0
IV Fosfomycin PK Study	27 August 2020

will be used in the lower airway. A fiberoptic bronchoscope will be inserted into the right middle lobe. Four 50-mL aliquots of sterile normal saline will be instilled into the right middle lobe and each specimen will be immediately aspirated and placed on ice. BAL samples for PK measures will be obtained  $\pm 15$  minutes from the subject's assigned sampling time. The start and stop times of BAL will be recorded on the eCRF.

Subjects will be continuously monitored during bronchoscopy. Blood pressure, heart rate, respiratory rate, and peripheral oxygen saturation will be recorded before and at the end of bronchoscopy. Subjects will undergo cardiac monitoring during bronchoscopy.

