14.3.5 Displays of Laboratory Results

14.3.5.1 Chemistry Results

Table 20: Chemistry Laboratory Results by Parameter, Severity, and Timepoint

[Implementation Note: If there are no subjects with an early termination visit, then that row will not be included in the table. If no values are missing for any parameter then that column will not be included in the table. If no values meet the criteria for the "Outside Normal Range" column then exclude column and corresponding footnote. Only Sodium, potassium, magnesium, calcium, and phosphorus are collected at the 2 hours prior to the assigned bronchoscopy timepoint, summaries for all other parameters will not include the "2 hours prior to the assigned bronchoscopy" row]

Chemistry Parameter		N	one	Outsid Ra	e Normal nge ^a	M Gra	ild/ de 1	Mod Gra	erate/ 1de 2	Sev Gra	/ere/ ade 3	Mis	sing
Timepoint	Ν	n	%	n	%	n	%	n	%	n	%	n	%
Chemistry - Any Parameter													
Baseline	х	х	х	NA	NA	х	х	х	х	х	х	х	х
2 hours prior to the assigned bronchoscopy ^b	х	х	х	х	х	x	х	x	х	x	х	х	х
Prior to Discharge (Day 2)													
Early Termination Visit													
Max Severity Post Baseline													
Sodium - Increase													
Baseline	х	х	х	NA	NA	х	х	х	х	х	х	х	х
2 hours prior to the assigned bronchoscopy ^b	х	х	х	х	х	х	х	х	х	х	х	х	х
Prior to Discharge (Day 2)													
Early Termination Visit													
Max Severity Post Baseline													
Sodium - Decrease													
Baseline	х	х	х	NA	NA	х	х	х	х	х	х	х	х
2 hours prior to the assigned bronchoscopy ^b	х	х	х	х	х	х	х	х	х	х	x	х	х
Notes: N = Number of subjects in the Safety Population ZTI-01 dose. The "Max Post Baseline" rows indicate ^a Post-dose measurements that were outside the normal "Outside Normal Range"	with clinical safety the maximum sever range but did not me	labs result ity experie eet the defi	s at the res nced by ea inition for a	pective stu ch subject an AE due	dy timepoint at any timepo to the value b	. Baseline bint post b being less	= The mos aseline, inc than or equ	t recent m cluding uns al to the n	easuremen scheduled a neasuremer	t prior to s assessment at baselin	tart of infu is. ne will be (sion of the	first 1 as

^b Only Sodium, potassium, magnesium, calcium, and phosphorus are collected at the 2 hours prior to the assigned bronchoscopy timepoint.

Table 21:	Chemistry Laboratory Summary Statistics by Parameter a	nd Timepoint
-----------	--	--------------

			М	easurement		Change from Baseline				

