Timepoint	Ν	Mean	SD	Median	Min, Max	Mean	SD	Median	Min, Max	
Sodium (mEq/L)										
Baseline	Х	X.X	X.X	X.X	X.X, X.X	-	-	-	-	
2 hours prior to the assigned bronchoscopy	Х	X.X	X.X	X.X	X.X, X.X	X.X	X.X	X.X	x.x, x.x	
Prior to Discharge (Day 2)										
Potassium (mEq/L)										
Baseline	Х	X.X	X.X	X.X	X.X, X.X	-	-	-	-	
2 hours prior to the assigned bronchoscopy	х	X.X	X.X	X.X	X.X, X.X	X.X	X.X	X.X	X.X, X.X	
Prior to Discharge (Day 2)										
Magnesium (mg/dL)										
Baseline	X	X.X	X.X	X.X	X.X, X.X	-	-	-	-	
2 hours prior to the assigned bronchoscopy	X	X.X	X.X	X.X	X.X, X.X	X.X	X.X	X.X	x.x, x.x	
Prior to Discharge (Day 2)										
Calcium (mg/dL)										
Baseline	х	X.X	X.X	X.X	X.X, X.X	-	-	-	-	
2 hours prior to the assigned bronchoscopy	х	X.X	X.X	X.X	X.X, X.X	X.X	X.X	X.X	X.X, X.X	
Prior to Discharge (Day 2)										
Phosphorus (mg/dL)										
Baseline	Х	X.X	X.X	X.X	X.X, X.X	-	-	-	-	
2 hours prior to the assigned bronchoscopy	Х	X.X	X.X	X.X	X.X, X.X	X.X	X.X	X.X	x.x, x.x	
Prior to Discharge (Day 2)										
Albumin (g/dL)										
Baseline	Х	X.X	X.X	X.X	x.x, x.x	-	-	-	-	
Prior to Discharge (Day 2)	Х	X.X	X.X	X.X	X.X, X.X	X.X	X.X	X.X	x.x, x.x	
Random Glucose (mg/dL)										
Baseline	X	X.X	X.X	X.X	X.X, X.X	-	-	-	-	
Notes: N = Number of subjects in the Safety Populati ZTI-01 dose.	ion with clinical s	afety labs resu	lts at the respec	tive study timepo	int. Baseline = The	most recent mea	surement prior	to start of infusi	on of the first	

Table 22: Hematology Laboratory Results by Parameter, Severity, and Timepoint

[Implementation Note: If there are no subjects with an early termination visit, then that row will not be included in the table. If no values are missing for any parameter then that column will not be included in the table. If no values meet the criteria for the "Outside Normal Range" column then exclude column and corresponding footnote.]

Hematology Parameter		No	one	Outside Rai	e Normal nge ^a	M Gra	ild/ 1de 1	Mod Gra	erate/ 1de 2	Sev Gra	vere/ ade 3	Mis	sing
Timepoint	Ν	n	%	n	%	n	%	n	%	n	%	n	%
Hematology - Any Parameter													
Baseline	х	х	х	NA	NA	х	x	х	х	х	х	x	x
Prior to Discharge (Day 2)	х	х	х	х	x	х	x	х	х	х	х	x	х
Early Termination Visit													
Max Severity Post Baseline													
Hemoglobin - Increase													
Baseline	x	х	х	NA	NA	х	x	х	х	х	х	x	x
Prior to Discharge (Day 2)	х	х	х	х	х	х	x	х	х	х	х	x	х
Early Termination Visit													
Max Severity Post Baseline													
Hematocrit - Increase													

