10.1 Disposition of Subjects

14.3.1.2 Unsolicited Adverse Events

Figure 3: Incidence of Related Adverse Events by MedDRA System Organ Class and Severity – All Subjects

[Implementation Note: Show one bar graph, include all subjects]

Figure 4: Frequency of Related Adverse Events by MedDRA System Organ Class and Maximum Severity – All Subjects

[Implementation Note: Show one bar graph, include all subjects]

Figure 5:Chemistry Laboratory Results by Scheduled Timepoints: Box Plot of Change from
Baseline by Laboratory Parameter – Sodium

[Implementation Note: For Laboratory Parameters with more than one timepoint, use lines to connect the 25th and 75th percentiles and median. Omit lines if Laboratory Parameter measured only one post dose timepoint]

Time Post Start of Infusion

Figures with Similar Format:

Figure 6:	Chemistry Laboratory Results by Scheduled Timepoints: Box Plot of Change from Baseline by Laboratory Parameter – Potassium
Figure 7:	Chemistry Laboratory Results by Scheduled Timepoints: Box Plot of Change from Baseline by Laboratory Parameter – Magnesium
Figure 8:	Chemistry Laboratory Results by Scheduled Timepoints: Box Plot of Change from Baseline by Laboratory Parameter – Calcium
Figure 9:	Chemistry Laboratory Results by Scheduled Timepoints: Box Plot of Change from Baseline by Laboratory Parameter – Phosphorus

Figure 10:	Chemistry Laboratory Results by Scheduled Timepoints: Box Plot of Change from Baseline by Laboratory Parameter – Albumin
Figure 11:	Chemistry Laboratory Results by Scheduled Timepoints: Box Plot of Change from Baseline by Laboratory Parameter – Random Glucose
Figure 12:	Chemistry Laboratory Results by Scheduled Timepoints: Box Plot of Change from Baseline by Laboratory Parameter – BUN
Figure 13:	Chemistry Laboratory Results by Scheduled Timepoints: Box Plot of Change from Baseline by Laboratory Parameter – Total Protein
Figure 14:	Chemistry Laboratory Results by Scheduled Timepoints: Box Plot of Change from Baseline by Laboratory Parameter – Creatinine
Figure 15:	Chemistry Laboratory Results by Scheduled Timepoints: Box Plot of Change from Baseline by Laboratory Parameter – Triglycerides
Figure 16:	Chemistry Laboratory Results by Scheduled Timepoints: Box Plot of Change from Baseline by Laboratory Parameter – Total Cholesterol
Figure 17:	Chemistry Laboratory Results by Scheduled Timepoints: Box Plot of Change from Baseline by Laboratory Parameter – CPK

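### The pre-bronchoscopy electrolyte row in SAP Tables 20 and 21 mixes draws taken after two doses with draws taken after three, and needs a before/after Dose 3 split

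*Protocol*

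**What the plan says.** Protocol 8.2.1 sets the draw of the five electrolytes (sodium, potassium, magnesium, calcium and phosphorus) at "approximately 2 hours prior to the assigned bronchoscopy timepoint". No window is given for the word approximately. Protocol 8.2.2 fixes the reference points: "The bronchoscopy sampling times will be at 30 minutes, 1 hour 15 minutes, 2, 5, and 8 hours from the start time" of the third infusion, and "A total of 6 subjects will be assigned to each of the five BAL sampling times". The Protocol Summary gives the dosing clock: "Three IV doses of ZTI-01 will be administered every 8 hours (hours 0, 8, and 16 during the Treatment Phase").

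The pooling is in the SAP. The Table 20 shell notes that "Only Sodium, potassium, magnesium, calcium, and phosphorus are collected at the 2 hours prior to the assigned bronchoscopy timepoint", and both Table 20 (severity grades) and Table 21 (values and change from baseline) carry one row labelled "2 hours prior to the assigned bronchoscopy" for the Safety Population. Neither the shells nor SAP 9.6 divides that row by BAL group or by number of doses received. SAP 9.6 takes as baseline the last value before the first infusion begins. Figures 5 to 9 show the same change from baseline as box plots; the surviving axis text in the Figure 5 shell is "Time Post Start of Infusion".

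**The concern.** The draw is tied to the procedure, and the procedure time is randomised, so subjects in one row have had different amounts of drug. Protocol 2.3.1 links the sodium load to hypokalaemia, and Protocol 6.2 puts that load at 1980 mg per dose. Apart from baseline and discharge, this is the only scheduled electrolyte sample; Appendix C lists one electrolytes-only tube. A mean change or a grade count taken across the row belongs to no defined exposure.

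The SAP is more careful elsewhere. Vital signs (Tables 28 and 29) are shown by dose and by time from the start of each infusion, and adverse events (Table 12) by infusion interval. Listings 10 to 12 give actual time after the numbered infusion, whereas the chemistry listing (Listing 9) has only a general actual-timepoint column. Dose-relative timing is therefore least explicit for the panel in which it varies most between subjects.

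**Working it through.** The documents state no draw time relative to Dose 3, so there is no figure of theirs to reproduce on the timing itself.

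**Draw times.** Inputs: BAL times and six subjects per group (Protocol 8.2.2), the 2-hour lead (Protocol 8.2.1), and doses at hours 0, 8 and 16 (Protocol Summary). Draw from Dose 3 start = BAL time − 2 h; study hour = 16 + that value.

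| BAL group | Draw from Dose 3 start | Study hour | Doses received | Time since latest infusion start | n |
|---|---|---|---|---|---|
| 0.5 h | −1.5 h | 14.5 | 2 | 6.5 h | 6 |
| 1.25 h | −0.75 h | 15.25 | 2 | 7.25 h | 6 |
| 2 h | 0 h | 16 | 2 (third about to start) | 8 h | 6 |
| 5 h | +3 h | 19 | 3 | 3 h | 6 |
| 8 h | +6 h | 22 | 3 | 6 h | 6 |

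The span is 6 − (−1.5) = 7.5 h. After two doses: 3 × 6 = 18 of 30 (60%), with 2 × 1980 = 3960 mg sodium given. After three: 2 × 6 = 12 of 30 (40%), with 3 × 1980 = 5940 mg.

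**Sensitivity to the missing window.** If approximately means ±15 min (an assumption), the range is −1.75 to +6.25 h; if ±30 min, −2.0 to +6.5 h. In both cases only the 2 h group can fall on either side of the start of Dose 3. A before/after split by actual time could therefore run from 18 and 12 to 12 and 18.

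**What the pooled mean estimates.** Let D be the mean change from baseline after two doses and E the additional change 3 to 6 h after Dose 3 starts. Take D as common to the groups, which randomisation supports, and as stable over the earlier draws. Then

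pooled mean = [18 × D + 12 × (D + E)] / 30 = D + 0.4 × E.

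The factor 0.4 comes from the allocation alone.

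**What the pooled grade count estimates.** If the proportions with a given grade are p2 after two doses and p3 after three, the row shows 0.6 × p2 + 0.4 × p3, which is neither.

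**Information per sub-row.** The chance of at least one event is 1 − (1 − p)^n. For n = 30 this gives 78.5% at p = 5% and 95.8% at p = 10%, reproducing the 79% and 96% in Protocol Table 8. For n = 18 it gives 60.3% and 85.0%; for n = 12, 46.0% and 71.8%.

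**The case against.** The best defence is that the row answers the question for which the sample was taken. The draw is a safety check before bronchoscopy, not a dose-timed measurement, and electrolytes about two hours before the procedure is a coherent quantity under an honest label. This stands, and it is why the pooled row should stay. A reader might infer that it should be removed; the documents do not support that.

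A reader might also take this row to be the trial's main hypokalaemia summary. No section ranks it so. Both tables have a pre-discharge row, taken when discharge is at least 12 h after the start of Dose 3 (Protocol Section 4), and Table 20 has a maximum-severity row. Protocol 9.2.3 enters every post-dose laboratory abnormality of Grade 1 or higher as an adverse event, and Table 12 separates events by infusion interval. These displays limit the harm considerably, but they do not repair the row. The discharge sample is not a 3 to 6 h value. It is also not wholly uniform: under Protocol 8.2.2, a Grade 2 result in the 30 or 75 minute group comes before Dose 3 and ends dosing. Table 12 holds no continuous values.

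Two further stronger readings fail. One is that the row shows only 40% of any potassium fall. Baseline precedes Dose 1, so the 18 earlier subjects already carry the two-dose change; only the extra Dose 3 effect is scaled by 0.4. The documents give no size for that effect, so no figure in mEq/L can be attached. The other is that this row must occupy five positions on the axis of Figures 5 to 9. The plots are not visible, and their titles refer to scheduled timepoints, which fits a categorical axis.

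It is also fair that 24 of 30 subjects are 6 to 8 h from their latest infusion start, so time since dose is fairly similar. Cumulative dose still differs.

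**Conclusion.** The point holds for one descriptive row and its box-plot counterparts. That row pools about 18 subjects sampled after two doses with 12 sampled after three. Its mean change is the two-dose change plus 0.4 of any additional Dose 3 effect, and its grade counts cannot be read as a rate for either exposure. The wider hypokalaemia assessment survives, and since the study tests no hypotheses (Protocol 11.1), no formal inference is affected. This is a cheap improvement in interpretability.

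The conclusion rests on nominal draw times, on the planned six evaluable subjects per group, and on a common two-dose change across groups. The Safety Population may exceed 30 because non-evaluable subjects are replaced, so 18 and 12 is the planned split and not a guaranteed one.

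**What to change.** In Tables 20 and 21, keep the pooled row as the summary of the pre-bronchoscopy check and add beneath it two sub-rows: draws before and draws after the start of Dose 3. Make the matching split in Figures 5 to 9. Classify by actual draw time where it is recorded, and otherwise by BAL group (30 min, 75 min and 2 h against 5 h and 8 h). Give Listing 9 the same column for actual time after the numbered infusion that Listings 10 to 12 already have.

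No new sample or procedure is needed, and the draw time and halting rule are untouched. BAL group is already in Listing 9. Recorded clock times are expressly required for PK and BAL samples (Protocol 8.2.3) but not stated as plainly for chemistry, hence the fallback. SAP Section 15 allows an addendum before data lock. The downside is sub-rows of about 18 and 12 subjects, with the lower chance of seeing an uncommon event shown above; the retained pooled row keeps the full count.

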#### 8.2.2. Bronchoscopy and Bronchoalveolar Lavage (BAL)

Each subject will be assigned to one bronchoscopy sampling timepoint. The bronchoscopy sampling times will be at 30 minutes, 1 hour 15 minutes, 2, 5, and 8 hours from the start time of the third (last) infusion of ZTI-01. A total of 6 subjects will be assigned to each of the five BAL sampling times.

Sodium, potassium, magnesium, calcium, and phosphorus will be measured approximately 2 hours prior to each subject's bronchoscopy timepoint. Subjects with grade 2 or higher abnormalities (Appendix B) in these electrolytes will not receive any further study product and will not undergo bronchoscopy.

Bronchoscopy will be performed in a standardized fashion according to the MOP. Topical lidocaine will be applied to the upper airways to prepare subjects for bronchoscopy. If needed, 1.0% percent lidocaine

CONFIDENTIAL

DMID Protocol 16-0058	Version 9.0
IV Fosfomycin PK Study	27 August 2020

will be used in the lower airway. A fiberoptic bronchoscope will be inserted into the right middle lobe. Four 50-mL aliquots of sterile normal saline will be instilled into the right middle lobe and each specimen will be immediately aspirated and placed on ice. BAL samples for PK measures will be obtained  $\pm 15$  minutes from the subject's assigned sampling time. The start and stop times of BAL will be recorded on the eCRF.

Subjects will be continuously monitored during bronchoscopy. Blood pressure, heart rate, respiratory rate, and peripheral oxygen saturation will be recorded before and at the end of bronchoscopy. Subjects will undergo cardiac monitoring during bronchoscopy.

